## **10. Patient Withdrawal & Replacement**

### **10.1 Patient Withdrawal**

Participation in the study is strictly voluntary. The patients have the right to withdraw from the study at any time for any reason, without the need to justify. The Investigator also has the right to withdraw patients in case of safety concerns, protocol deviations or administrative reasons. Since an excessive rate of withdrawals can render the study uninterpretable, the unnecessary withdrawal of patients must be avoided.

Reasons of withdrawal include, but are not limited, to the following:

- Patient decision
- Lost to follow-up, death

- Any AE, laboratory abnormality or illness which, in the opinion of the Investigator, indicates that continued treatment with study therapy and participation in the trial is not in the best interest of the subject.
- Major protocol deviation: e.g. lack of compliance with scheduled visits, non-compliance with study treatment, treatment with prohibited medication during the study (see 22)
- Any deterioration in cardiac status
- ALT or AST > 8 x ULN; or if ALT or AST > 5xULN for more than 2 weeks; or if ALT or AST > 3xULN and bili (total) > 2xULN (or INR>1.5); or ALT or AST > 3xULN and symptoms (Right Upper Quadrant pain, nausea, ...)
- Investigator's decision for any other reason

If a patient discontinues the study, the Investigator will make reasonable efforts to obtain the reason and to perform all protocol-defined end of study assessments as soon as possible. The reason and circumstances for premature discontinuation (e.g. consent withdrawal, AE, lost to follow up, etc.), and the date of withdrawal must be documented in the eCRF. If a patient discontinues the study for safety reasons, the outcome must be known.

In the case of withdrawal due to pregnancy (see paragraph 6.2.1), the patient will be followed until outcome, i.e. at least on a quarterly basis for follow-up evaluation of the pregnancy, foetus, delivery and new born. In the case of withdrawal due to an AE the patient will be followed until resolution of the AE, or until in the opinion of the Investigator the event has stabilized, and the patient is referred to their primary physician for appropriate management of the ongoing event. Reasonable efforts will be made to contact a patient who fails to attend any follow-up appointments, in order to ensure that he/she is in satisfactory health.

Health data and biological samples collected during the whole participation of the patient will be analysed at the end of the study, and the biological samples stored up to one year after the completion of the study and destroyed.

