### 5.3.2 Retest visit (additional visit during screening process)

A retest visit could be performed if requested by Investigators and/or Sponsor to confirm/invalidate abnormal biological values at screening process. This retest will be mandatory if the total duration of the screening period exceed 4 weeks (i.e. inclusion/non-inclusion criteria related to safety laboratory tests have to be checked with results of less than 4 weeks before randomization).

The randomization could be done only after receipt of the retest reports and validation of the results by the Investigators and/or Sponsor Referent Physician.

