#### 5.3.7 *Unscheduled/safety Visits*

During the all treatment and the follow-up period, the Investigator may conduct unscheduled visit that may perform again study procedures, including vital signs assessments, blood sample taken and physical examination. These visits will have to be motivated by the Investigator in the aim of guarantee the safety of the patients.

Specific events listed bellow, will automatically generate an Unscheduled/safety visit:

- ALT increase of 2 times of the baseline value at V0: A safety visit has to be performed 15 days later. A blood taken will be performed to check the ALT level.
- ALT increase of 5 times the upper limit of the normal range (ULN): A safety visit has to be performed 15 days later. A blood taken will be performed to check the ALT level

Please refer to paragraph 10 for withdrawal criteria.

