### *6.4.3 Safety monitoring*

The DSMB will be provided in a semi-unblinded way (treatment A, B, C), with ECG parameters (heart rate, QT, QTc Bazett and Fridericia, delta QTc Bazett and Fridericia, PR interval, ECG interpretation) and main laboratory assessments. In addition, they will be provided with a listing of all AE/SAEs. The DSMB may request a break of the blind, and SUSAR will be provided unblinded.

The frequency of the DSMB and the criteria for ad-hoc meeting will be specified in the DSMB charter.

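### Entry allows ALT up to 10xULN and any AST, yet the listed liver withdrawal limits start at 5xULN and make no allowance for a value already raised before dosing

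*Protocol*

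**What the plan says.** **Entry.** Inclusion criterion 4 (Protocol synopsis and section 4.2.1) requires ALT below 10xULN before randomization. Neither the inclusion nor the exclusion list names AST, although AST is measured at screening and V0 (Protocol Tables 1 and 8). SAP section 3.4.1 records no change to the ALT limit for protocol versions 5.0 and 5.1.

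**Withdrawal.** Protocol section 10.1 lists "ALT or AST > 8 x ULN; or if ALT or AST > 5xULN for more than 2 weeks". It also has limits at 3xULN combined with bilirubin, INR or symptoms. The list opens with "Reasons of withdrawal include, but are not limited, to the following", and the same section says that "the unnecessary withdrawal of patients must be avoided".

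**Safety visits.** Section 5.3.7 calls for a visit after "ALT increase of 2 times of the baseline value at V0" and, separately, at an absolute 5xULN for ALT. Each is a recheck 15 days later. The section closes with "Please refer to paragraph 10 for withdrawal criteria".

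**Oversight.** Under section 6.3 the investigator rates every safety variable for clinical relevance and repeats relevant abnormalities. Under section 5.3.2 a retest during screening needs "validation of the results by the Investigators and/or Sponsor Referent Physician" before randomization. Under section 6.4.3 the DSMB receives ECG parameters "and main laboratory assessments".

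**The concern.** A stopping limit is meant to detect liver injury arising on treatment. If the entry limit lies above it, the limit can be met by disease the patient brought into the trial, and it no longer separates the two. Sites must then decide for themselves. One may stop a stable patient at 8.5xULN because the number is on the list. Another may continue the same patient because unnecessary withdrawal is to be avoided. Both would be following section 10.1. SAP section 3.5 reports 92 sites, so uniform reading cannot be taken for granted.

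At stake are consistent use of a liver safety limit in a liver-disease trial, and some early discontinuations that might have been avoided.

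**Working it through.** **1. Thresholds side by side** (inclusion criterion 4 against the two stand-alone limits in section 10.1, for a stable pre-dose value):

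| Pre-dose value | Eligible? | Above 8xULN | Above 5xULN for more than 2 weeks |
|---|---|---|---|
| ALT up to 5xULN | yes | no | no |
| ALT above 5, up to 8xULN | yes | no | met once 14 days are exceeded |
| ALT above 8, below 10xULN | yes | met at entry | met once 14 days are exceeded |
| ALT 10xULN or more | no | – | – |
| AST above 5, up to 8xULN | yes (no limit) | no | met once 14 days are exceeded |
| AST above 8xULN | yes (no limit) | met at entry | met once 14 days are exceeded |

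**2. Timing of the two-week limit.** The study procedures in the synopsis place screening 2 to 4 weeks before V0 with a historical biopsy and 2 to 8 weeks before V0 otherwise, that is 14 to 28 or 14 to 56 days. If pre-dose values count, any screening period longer than 14 days lets a stable value meet the limit by V0. The synopsis also mentions a selection period as short as 3 days. In that case V1 is the fallback: 28 − 3 = 25 to 28 + 3 = 31 days after V0, both more than 14.

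**3. Does other text resolve the overlap?** The baseline-relative trigger in section 5.3.7 prompts a visit only and does not modify section 10.1. The 5xULN trigger is absolute and names ALT alone. Sections 5.3.2, 6.3 and 6.4.3 provide review, but none says how a raised pre-dose value is to be set against the section 10.1 limits.

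**4. How many patients?** This cannot be derived. The figures below rest on assumed shares, which have no basis in the documents. Of the 247 randomised (SAP section 3.5), a share of 1%, 5% or 10% above 5xULN before dosing would be 2.5, 12.4 or 24.7 patients in the overlap. Being in the overlap does not mean being withdrawn.

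**5. Recruitment cost of a 5xULN cap.** SAP section 3.5 reports 868 screened and 247 randomised. Screen failure is (868 − 247)/868 = 621/868 = 71.5%, which reproduces the stated 72%. Screened per randomised patient is 868/247 = 3.51. The target was 225.

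| Assumed share excluded | Remaining of 247 | Shortfall against 225 | Extra screened |
|---|---|---|---|
| 1% | 244.5 | none | 0 |
| 5% | 234.7 | none | 0 |
| 10% | 222.3 | 2.7 (about 3) | 2.7 × 3.51 = 9.5 (about 10) |

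**The case against.** The strongest reply is that the protocol leaves these decisions to clinical judgement on purpose. Section 10.1 gives reasons, not orders, and discourages unnecessary withdrawal. Exclusion criterion 9 lets an investigator decline anyone whose condition might stand in the way of completing the study, which covers a patient already past a listed limit. Section 6.3 requires relevant abnormalities to be rated and repeated. Any error is also on the protective side, since it stops drug. All of this stands, and it is why the consequence is minor. It does not remove the overlap: discretion is not an exception for raised baselines, and inclusion criterion 4 expressly accepts ALT up to 10xULN.

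Four stronger readings are tempting but not supported:

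- *Withdrawal is mandatory above these limits.* Section 5.3.7 does refer to section 10 for criteria, but section 10.1 itself does not require withdrawal.
- *AST at entry is uncontrolled.* There is no numeric limit, but exclusion criterion 9 is a discretionary control.
- *A raised V0 value starts the 15-day recheck, so the two-week limit is met at day 15.* Section 5.3.7 covers the treatment and follow-up periods and speaks of an "ALT increase of 2 times of the baseline value at V0" and likewise of an increase to 5xULN. A stable pre-treatment value is arguably not an increase.
- *The primary result is biased or loses power.* Sections 5.3.4 and 10.1 ask for end-of-treatment assessments after early withdrawal. SAP section 4.1.6.3 uses biopsies taken at early discontinuation, and only a patient left without a result is counted as a non-responder. Nothing indicates a difference between arms.

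**Conclusion.** The point holds as a conflict between two stated numeric thresholds. A patient can be eligible and already meet a listed withdrawal reason before the first dose: ALT above 8 and below 10xULN, or AST above 8xULN. For stable values above 5xULN, the two-week limit can be met by V0 if pre-dose samples count, and otherwise by V1.

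The consequence is minor: uneven application of a liver stopping limit and possible avoidable discontinuation. How often this occurs is unknown. The conclusion rests on reading the limits literally, as absolute multiples of ULN. One caveat applies: the protocol supplied is version 5.0, while SAP section 2 refers to version 5.1. The SAP shows the ALT entry limit unchanged, but section 10.1 of version 5.1 could not be checked.

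**What to change.** In inclusion criterion 4 (synopsis and section 4.2.1), require both ALT and AST at or below 5xULN before randomization. Entry then lies below both stand-alone limits, and section 10.1 can stay as it is.

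**Cost.** This is a short text change. Both enzymes are already measured at screening and V0, so no procedure is added. Eligibility narrows slightly, by an unknown amount. Against the 225 target, the assumed 1% and 5% exclusions need no replacement, and 10% needs about 3 patients, or about 10 screened. Replacing every excluded patient up to 247 would cost more, but the plan did not require 247.

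**Limits of the fix.**

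- It does not reach the limit combining 3xULN with raised bilirubin. Inclusion criterion 4 admits Gilbert's patients with bilirubin of 35 µmol/L or more and no upper bound, so some with ALT or AST above 3xULN could meet that limit before dosing, depending on the laboratory's ULN.
- A patient entering at 5xULN can still drift slightly above it.
- The SAP already reports 247 randomised, so an entry change cannot alter their handling. For them, a count per arm of baseline ALT or AST above 5xULN and 8xULN, with early stops and reasons, would be an optional addition to SAP section 5.2.3.9. It would change no result.

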## **10.2 Unblinding Process**

### *10.2.1 Unblinding for emergency*

The code breaks will be available 24 hours a day and 7 days a week using an Interactive Web Response System (IWRS) implemented via the eCRF.

The IWRS will require an access code/password/PIN and are only available to staff members named on the delegation log for the trial recorded in the Trial Master file of each site.

The Investigators and delegated members with unblinding responsibilities are responsible for testing their username and password prior to the treatment of subjects to ensure unblinding is possible, or for ensuring appropriately trained staff members are available to action code breaks when required for medical emergencies which may be required out of normal working hours.

Sealed envelopes containing the code-break information will be provided to the Pharmacovigilance and safety Institution (Stragen, see 2.3).

Details of any emergency unblinding shall be documented fully in the Sponsor file, Investigator TMF and Pharmacy and Site File(s). This includes, but may not be limited to:

- 1) Date,
- 2) Subject details,

- 3) Reason for unblinding,
- 4) The results,
- 5) Name and role of the individual requesting the unblinding,
- 6) Name and role of the individual carrying out the unblinding.

If the Clinical Trials Pharmacy or an individual as named on the Delegation Log has performed the procedure, they will inform the Sponsor the trial identifier, subject number and name and title of the person making the request, but NOT the result. The details shall be included in the statistical report.

#### *10.2.2 Unblinding for DSMB*

Information will be provided to the DSMB unblinded, if requested.

To that effect, a named statistician not involved with the final data analysis or with the study, shall receive the relevant codes. A record shall be kept in the TMF of the name of the statistician, the date they were supplied the relevant code breaks and the location of the results. The unblinded data and the results supplied to the DSMB shall not be accessible by the Investigators or trial staff.

#### *10.2.3 Unblinding at end of trial*

The Statistical Analysis Plan shall be provided in the protocol or be finalized prior to the release of the randomization codes. Changes to the statistical analysis plan shall be version controlled. A record shall be kept in the Investigator TMF to confirm when the randomization code was requested and when provided.

## **11. Training & Information**

### **11.1 Training**

All persons involved in the study will be trained in an effort to standardize relevant methods, ratings and data capture and to prevent deviations.

### **11.2 Information of the Investigator**

The Investigator will receive all the relevant information for a safe use of the IMP as the study proceeds.

## **12. Records & Data**

### **12.1 Source Records & Data**

Source data are all the information in original records and certified copies of original records of clinical findings, observations, or other activities in the study, which are necessary for the reconstruction and evaluation of the study. The Investigator will permit study-related monitoring, audits, IEC reviews and regulatory inspections, with a direct access to all the required source records. For each patient enrolled, the Investigator will note in the source records that the patient participates in this study, and will record the following information: concomitant therapies, clinically significant adverse events and a statement at patient end of participation.

## **12.2 Case Report Forms**

Electronic Case Report Form (eCRF) will be provided by the CRO institution. The Investigator is responsible for maintaining adequate and accurate data into the eCRF which has been designed to record all observations and other data pertinent to the clinical investigation.

All data requested on the eCRF must be filled out completely by the Investigator or the Investigator team. All data captured for the study is planned to be electronic. The eCRF should be reviewed and electronically approved by the Investigator.

All missing data must be explained. If any entry error has been made, to correct such an error, enter the correct data above it. All such changes will be must electronically signed with the reason for the correction if necessary, by an authorized (Investigator/co-worker) person.

eCRF and all other source data must be easily accessible for review during the programmed monitoring visits. Once the clinical monitor has verified the contents of the completed eCRF against the source data, the system will be verified electronically by the clinical monitor for those pages. Queries may be raised if the data are unclear or contradictory, which must be addressed by the Investigator.

Patients are not to be identified in the eCRF by name or initials and birth date. Appropriate coded identification, e.g. patient number in combination with year of birth must be used.

## **13. Confidentiality**

### **13.1 Confidentiality of Patient Data**

The Investigator will ensure that the confidentiality of the patients' data is preserved. On eCRFs or any other documents for the Sponsor, the patients will not be identified by their names, but by their initials and numbers in the study. Documents not for transmission to the Sponsor, e.g. the confidential patient identification list and the signed informed consent forms will be maintained by the Investigator in strict confidence.

### **13.2 Confidentiality of Sponsor Data**

Any information on the IMP, this study and its results is confidential information. The Investigator, study site personnel and IEC members will not use, publish, or otherwise disclose any confidential information without the prior written authorization from the Sponsor. Any data, results, inventions and patents that may arise from this study will be the exclusive property of the Sponsor.

## **14. Reporting & Publication**

### **14.1 Study Report**

All the relevant data and information will be reported in a study report prepared by CRO (KEYRUS BIOPHARMA, section 2.2) and submitted to the Sponsor and the Investigators for review comments and signature. The final study report will be used for the further development of the IMP and regulatory submissions.

## **14.2 Disclosure of Data and Publications**

No information provided by INVENTIVA S.A. to the Investigators for the purposes of performing the study, will be published, or passed on to a third party, without prior written approval by INVENTIVA.

The Investigators will have full access to all of the study data and will take complete responsibility for the integrity of the data and the relevance of the data analysis and reporting.

After regulatory clearance, the study will be registered by the Sponsor in the ClinTrials.gov database. The Principal Investigator or anyone else working on the study will submit all proposed publications, papers, abstracts or other written materials or an outline of any proposed oral presentation related to the study to INVENTIVA S.A. at least 1 month prior to (i) submission of such written materials for publication, or (ii) any proposed oral disclosure to a third party. INVENTIVA S.A. shall have the right to comment on such written material/outline and to take any necessary action to protect its intellectual property; the Principal Investigator, in determining the final form of disclosure, shall consider such comments in good faith. Notwithstanding any of the above, the Principal Investigator or anyone else working on the Study may not include any confidential information unrelated to the study in any such publication or disclosure.

The Investigator will provide INVENTIVA S.A. with complete test results and all data derived from the study in accordance with the protocol.

Only INVENTIVA S.A. and its authorized contractor may make information obtained during the study available to regulatory agencies, except as required by regulation.

## **15. Record Keeping**

### **15.1 Study Site Records**

The Investigator is responsible for maintaining all the records which enable the conduct of the study at the study site to be fully understood. The study documentation and source records will be archived for the maximum period of time permitted by local requirements. The Investigator will complete the confidential patient identification list which provides the sole link between source records and anonymous eCRF data. The Investigator will retain this confidential list and the signed consent forms for at least fifteen years after the completion or discontinuation of the study. No study site records may be destroyed without prior written agreement between the investigator and the Sponsor. If the Investigator intends to assign the study documents to another party, or to move them to another location, the Sponsor must be notified.

### **15.2 Study Master File**

The Sponsor will archive the study master file in accordance with GCP and applicable regulatory requirements.

## APPENDIX A: WORLD MEDICAL ASSOCIATION DECLARATION OF HELSINKI

### **WMA Declaration of Helsinki - Ethical Principles for Medical Research Involving Human Subjects**

---

Adopted by the 18th WMA General Assembly, Helsinki, Finland, June 1964  
and amended by the:

29th WMA General Assembly, Tokyo, Japan, October 1975

35th WMA General Assembly, Venice, Italy, October 1983

41st WMA General Assembly, Hong Kong, September 1989

48th WMA General Assembly, Somerset West, Republic of South Africa, October 1996

52nd WMA General Assembly, Edinburgh, Scotland, October 2000

53rd WMA General Assembly, Washington DC, USA, October 2002 (Note of Clarification added)

55th WMA General Assembly, Tokyo, Japan, October 2004 (Note of Clarification added)

59th WMA General Assembly, Seoul, Republic of Korea, October 2008

64th WMA General Assembly, Fortaleza, Brazil, October 2013

#### **Preamble**

1. The World Medical Association (WMA) has developed the Declaration of Helsinki as a statement of ethical principles for medical research involving human subjects, including research on identifiable human material and data.

The Declaration is intended to be read as a whole and each of its constituent paragraphs should be applied with consideration of all other relevant paragraphs.

2. Consistent with the mandate of the WMA, the Declaration is addressed primarily to physicians. The WMA encourages others who are involved in medical research involving human subjects to adopt these principles.

#### **General Principles**

3. The Declaration of Geneva of the WMA binds the physician with the words,

1/8

“The health of my patient will be my first consideration,” and the International Code of Medical Ethics declares that, “A physician shall act in the patient's best interest when providing medical care.”

4. It is the duty of the physician to promote and safeguard the health, well-being and rights of patients, including those who are involved in medical research. The physician's knowledge and conscience are dedicated to the fulfilment of this duty.
5. Medical progress is based on research that ultimately must include studies involving human subjects.
6. The primary purpose of medical research involving human subjects is to understand the causes, development and effects of diseases and improve preventive, diagnostic and therapeutic interventions (methods, procedures and treatments). Even the best proven interventions must be evaluated continually through research for their safety, effectiveness, efficiency, accessibility and quality.
7. Medical research is subject to ethical standards that promote and ensure respect for all human subjects and protect their health and rights.
8. While the primary purpose of medical research is to generate new knowledge, this goal can never take precedence over the rights and interests of individual research subjects.
9. It is the duty of physicians who are involved in medical research to protect the life, health, dignity, integrity, right to self-determination, privacy, and confidentiality of personal information of research subjects. The responsibility for the protection of research subjects must always rest with the physician or other health care professionals and never with the research subjects, even though they have given consent.
10. Physicians must consider the ethical, legal and regulatory norms and standards for research involving human subjects in their own countries as well as applicable international norms and standards. No national or international ethical, legal or regulatory requirement should reduce or eliminate any of the protections for research subjects set forth in this Declaration.
11. Medical research should be conducted in a manner that minimises possible harm to the environment.
12. Medical research involving human subjects must be conducted only by

2/8

individuals with the appropriate ethics and scientific education, training and qualifications. Research on patients or healthy volunteers requires the supervision of a competent and appropriately qualified physician or other health care professional.

13. Groups that are underrepresented in medical research should be provided appropriate access to participation in research.

14. Physicians who combine medical research with medical care should involve their patients in research only to the extent that this is justified by its potential preventive, diagnostic or therapeutic value and if the physician has good reason to believe that participation in the research study will not adversely affect the health of the patients who serve as research subjects.

15. Appropriate compensation and treatment for subjects who are harmed as a result of participating in research must be ensured.

